14.2.1 ANALYSIS POPULATION

Clinical Study Protocol CAN version FINAL 2.0

All patients who have received at least one anaesthesia will be included in the population. Only observed data will be used.

Date: 28 Oct 2016 22 (31)

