11.5 RANDOMISATION AND BLINDING

The study patients will be randomly allocated to either propofol- or sevoflurane-group in a 1:1 ratio. The randomisation list is generated by computer in a permuted block fashion and transferred to a sequence of sealed, opaque, consecutively numbered envelopes. When a patient is considered eligible for the study and has given informed consent, randomisation is performed by opening the next envelope in sequence. Once assigned a treatment group by randomisation, a subject cannot be "unrandomised" or "de-registered" from the study population. Moreover, "cross-over" between treatment assignments (i.e. propofol to sevoflurane, or vice versa) will not be permitted.

Blinding is not applicable – open label study.

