14.1.2 DATABASE CLOSURE

When all patients have been completed (i.e. completion of follow-up 365 days post surgery), all data have been entered into the database, and all queries solved, the Database Closure procedures will start. Decisions will be made how to classify patients into analysis populations, and how to handle protocol violations and deviating or missing data. All decisions will be dated and documented in a Database Closure document. After that the database will be locked. Any changes in the database thereafter will be documented.

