14.2 STATISTICAL ANALYSIS

The clinical database will be transferred to the Sponsor by UCR. Tumour-specific data will be transferred to the Sponsor from the RCC quality registers for the Swedish study population. For other countries, there will be local procedures to capture this data and to have the information transferred to the Sponsor. Sponsor will then be responsible for linking these databases and will also do the statistical analysis.

Based on the experience from study start, the breast cancer cohort has higher recruitment-rate than the colo- and rectal-cancer cohorts. Accordingly, recruitment of breast cancer patients will be completed earlier. Due to this, the analysis of the breast cancer cohort will be made earlier than the other two cohorts. Based on the outcome of this analysis, decision will be taken about further recruitment in the study.

In the present study all endpoints will be evaluated by descriptive methods. All variables will be presented as aggregated data. Categorical variables will be summarised in frequency tables (presenting frequencies and proportions) by type of anaesthesia. The quantitative variables will be summarised by number of observations (n), mean, standard deviation (SD), median, minimum (min) and maximum (max) by anaesthesia. If applicable, separate summaries will be presented for patients receiving one, two or more anaesthesia, as well as pooled summaries. Graphical methods may be used wherever it is regarded as appropriate.

Overall survival (OS) and time to progress (TTP) will be presented as Kaplan-Meier curves together with median survival time and time to progression, respectively.

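### The only analysis population is defined by receipt of anaesthesia rather than by randomisation, and the protocol does not say that patients are compared in their allocated arm

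*Protocol*

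**What the plan says.** Section 14.2.1 of the protocol names one analysis population and ties it to treatment: "All patients who have received at least one anaesthesia will be included in the population. Only observed data will be used".

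Section 14.2 describes the grouping. Categorical variables are to be "summarised in frequency tables (presenting frequencies and proportions) by type of anaesthesia", and quantitative variables are grouped in the same terms. If applicable, "separate summaries will be presented for patients receiving one, two or more anaesthesia, as well as pooled summaries". Overall survival and time to progression follow in a separate paragraph as Kaplan-Meier curves, with no grouping stated.

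Section 11.5 points the other way. "Once assigned a treatment group by randomisation, a subject cannot be" taken out of the study population afterwards, and cross-over between the two hypnotics is ruled out. The envelope is opened once the patient is eligible and has consented, and the trial is open-label. Section 13.1 records the allocation and, separately, the hypnotic actually used.

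Section 14.1.2 places a further step after 365-day follow-up, data entry and query resolution: "Decisions will be made how to classify patients into analysis populations, and how to handle protocol violations and deviating or missing data".

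**The concern.** Section 9.1 calls randomisation the only study-specific procedure. It is also what separates this trial from the retrospective study in section 6.1.4, whose result the protocol describes as distorted by unevenly distributed confounders. The protection lasts only if everyone randomised is compared in the arm to which they were allocated.

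Three pieces of text leave that open:

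- Membership of the analysis population depends on something that happens after an allocation known to the staff.
- The grouping variable is not pinned to the allocation, although the data collection foresees that allocation and treatment may differ.
- The choice of population is made in one section and deferred to database closure in another.

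At stake is bias in a survival comparison whose target difference is 5 percentage points.

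**Working it through.** **1. The plan's own figure.** Inputs from section 14.3: 80% power, 5% significance (taken as two-sided, since sidedness is not stated), and five-year survival of 87% vs 82% (breast), 60% vs 55% (colon) and 70% vs 65% (rectal). Allocation is 1:1 (section 11.5). With HR = ln(p1)/ln(p2), Freedman's formula gives events d = (1.96 + 0.84)² × [(1 + HR)/(1 − HR)]², and N = d divided by the mean five-year probability of death.

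- Breast: HR 0.702, 256 events, 256/0.155 = 1,652
- Colon: HR 0.854, 1,275 events, 1,275/0.425 = 3,000
- Rectal: HR 0.828, 887 events, 887/0.325 = 2,729 (stated: 2,728)

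The sum is 7,381, against 7,378 stated. A pooled two-proportion formula gives 1,644 + 3,068 + 2,754 = 7,466, which is 1.2% higher. The margin is 8,000/7,378 = 1.084, the stated 8.4%. The sample size reproduces, and analysing all randomised patients does not change it.

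**2. Bias from dropping never-anaesthetised patients.** Suppose no true effect and survival p = 0.82 in both arms. The share never anaesthetised is e, and their survival is 20 points lower (0.62). The shares and the deficit are assumptions, because the protocol gives none. Survival in those kept is S(e) = (p − 0.62e)/(1 − e).

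- S(1%) = 0.8138/0.99 = 82.20%
- S(2%) = 0.8076/0.98 = 82.41%
- S(3%) = 0.8014/0.97 = 82.62%
- S(5%) = 0.7890/0.95 = 83.05%

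The false difference is therefore 0.00 points at 1% vs 1%, 0.21 at 2% vs 1%, 0.42 at 3% vs 1% and 0.85 at 5% vs 1%.

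**3. Bias if groups were formed by the hypnotic received.** Again assume no true effect, with a share c of the propofol arm switched to sevoflurane and survival of 0.62 in those switched. Propofol becomes (0.82 − 0.62c)/(1 − c), and sevoflurane becomes (0.82 + 0.62c)/(1 + c).

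- c = 2%: 0.8076/0.98 − 0.8324/1.02 = 82.41% − 81.61% = 0.80 points
- c = 5%: 0.7890/0.95 − 0.8510/1.05 = 83.05% − 81.05% = 2.0 points

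With a 10-point deficit the same shares give 0.40 and 1.00 points. Arm size cancels out of both formulas.

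**4. Cost of analysing by allocation.** If a share c of each arm receives the other drug, the 5-point difference shrinks to 5 × (1 − 2c). Each tumour group, at its own 80%-power size, then has this power:

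| Two-way cross-over (assumed) | Difference | Power |
|---|---|---|
| 1% | 4.90 points | 78.4% |
| 2% | 4.80 points | 76.7% |
| 5% | 4.50 points | 71.3% |
| 10% | 4.00 points | 61.1% |

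**The case against.** The strongest reply is that a reader might infer more than the text says.

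- **As-treated grouping.** Sections 6 and 9.1 name the randomised arms as propofol anaesthesia and sevoflurane anaesthesia, so the grouping phrase in 14.2 may simply mean the allocated arm. That is fair. As-treated grouping is a possible reading and not a stated rule, so the fault is ambiguity. Step 3 applies only under that reading.
- **Immortal time.** A second anaesthetic requires survival to that point, so survival curves split by number of anaesthetics would be biased. But the split is conditional, stands beside pooled summaries, and sits in the paragraph on tables and means. Nothing ties it to overall survival or time to progression.
- **Exclusions chosen with outcomes in view.** Section 14.1 keeps survival data out of the clinical database, and 14.1.2 requires decisions to be dated and documented before lock. The documents do not support a claim that populations are picked with survival known. What stands is that allocation is known by then, and that no sentence requires the choice to precede linkage.
- **Few patients affected.** Patients are already scheduled for elective surgery, cross-over is not permitted, and section 16.2 monitors compliance with the allocation. Both rates may be low. No rate is given, however, and 14.2.1 excludes these patients whatever the number.
- **Study versus analysis population.** Section 11.5 speaks of the study population, and section 18.1 requires a CRF for every randomised patient, so nobody is lost from the record. The record is kept, but 14.2.1 still leaves the patient out of the comparison.
- **A matter for the SAP.** Silence on intention-to-treat could be filled there. The exclusion is different, because the protocol states it as a rule.

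**Conclusion.** The point holds in limited form. Section 14.2.1 makes the only analysis population depend on an event after open-label randomisation, against the aim of section 11.5. Section 14.2 leaves allocated or received grouping unclear, and section 14.1.2 defers a decision that 14.2.1 has already taken. As written, the rules do not secure the randomised comparison.

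It would go too far to say that they undo the randomisation. The stated exclusion alone gives no bias if it is equal between arms, and 0.2 to 0.9 points under the assumed imbalances (2-5% vs 1%, 20-point deficit, 82% survival). The 0.8 to 2.0 points from as-received grouping need both that reading of 14.2 and one-way, prognosis-linked switching of 2-5% with the same deficit. All these rates are assumptions. Against a 5-point target, the lower figures are minor and the upper ones are not.

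**What to change.** - **Section 14.2.1:** state that the primary overall survival analysis includes all randomised patients in the arm allocated by the envelope, with time counted from randomisation and censoring at the last date known alive. The time origin has to be stated because the objectives count survival from surgery, which a never-operated patient does not have.
- **Sensitivity analyses:** use the anaesthetised set and the hypnotic actually given here.
- **Section 14.2:** say that groups are the allocated arms, and that the split by number of anaesthetics is descriptive and not used for overall survival or time to progression.
- **Section 14.1.2:** remove the decision on analysis populations, or require it to be fixed before survival data are linked.

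The cost is mainly wording, and the planned 8,000 stands. Power falls slightly through dilution, to about 78% at an assumed 1% two-way cross-over and 77% at 2%. Vital status must also be obtained for randomised patients who were never anaesthetised. That takes most care outside Sweden and Poland, where section 14.1 says that no personal identification number is captured.

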14.3 DETERMINATION OF SAMPLE SIZE

A clinically relevant absolute difference in five-year-survival would be 5%-units. Based on data from our retrospective study, we will have 80% power to detect a difference of 5%-units with a *P*-value of <0.05 if including 7,378 patients (see table below). By adding 8.4% more patients to the inclusion of 8,000 patients, we will have a reasonable safety margin for loss of patients or technical errors.

In-text table 14-1– tumor specific sample size calculation:

80% power and 5% significance demands for

Breast cancer with an expected 5-year survival of 87% vs 82% a number of:
Colon cancer with an expected 5-year survival of 60% vs 55% a number of:
Rectal cancer with an expected 5-year survival of 70% vs 65% a number of:
2 728 pts
Margin for loss of patients or technical errors

Total

8 000 pts

15 DIRECT ACCESS TO SOURCE DATA/DOCUMENTS

The Investigator(s)/institution(s) will permit study-related monitoring, audits, IEC review and regulatory inspection(s), providing direct access to source data/hospital records. The Sponsor verifies that each patient has consented in writing to direct access to the original source data/hospital records by the use of written patient information and signed Informed Consent.

In connection with on-site visits, the data recorded in the CRFs by the site will be controlled for consistency with the source data/hospital records by the study monitor (source data verification) for a random sample of patients. Any discrepancies of data will be documented and explained in the monitoring reports. The monitoring procedures including the level of Source Data Verification will be described in a study-specific Monitoring Plan which will be compiled in collaboration with the Sponsor.

16 QUALITY CONTROL AND QUALITY ASSURANCE

16.1 SOURCE DATA

Generally, the Medical Records / laboratory reports / anaesthetic reports will serve as source data. CRF can also be used as source data.

Following general Definition of Source Data location will apply for all sites and thus is no site-specific document made:

- The randomization sheet which is included in the randomization envelope is the source for randomization data. This sheet is filed in Investigators File.
- Date of signed Informed Consent is noted on the originally signed document. This serve as source for data of consent-data.
- Medical Notes is seen as source data for all other variables.

A site-specific Origin of Source Data-log needs to be compiled at the site if there are changes to these general Source Data location procedures.

Clinical Study Protocol CAN version FINAL 2.0

Date: 28 Oct 2016 23 (31)

The following minimum amount of information should be recorded in the hospital records:

- Clinical study number.
- Subject identification.
- Date when patient information was given and when signed Informed Consent was obtained.
- Diagnosis.
- Fulfillment of eligibility criteria.

16.2 MONITORING

In accordance with the principles of Good Clinical Practice (GCP), monitoring of the study will be arranged by the Sponsor. UCR has been appointed by the Sponsor to monitor this study for the Swedish sites and for the central monitoring of the database - see below. For other participating countries, the Sponsor will appoint local monitoring organisation to perform on-site monitoring activities and regular contacts. During the study, the Monitor will have regular contacts with the study site(s), including visits to ensure that the study is conducted and documented properly in compliance with the protocol, GCP and applicable regulatory requirements.

Both centralized monitoring activities and on-site monitoring activities will be used in this project. It has been decided that the major part of the monitoring will be made by centralized methods together with regulary telephone contacts with site but with limited on-site activities. This decision is based on the nature of the study – observational with no other study specific procedures than the randomization. Additionally, the investigational products used are well established within clinical practice since many years and with documented safety profile.

Each site will have a site initiation (can be organised as multi-centre initiation meeting or web-based training) with focus on providing information about study objectives, study procedures and CRF-training. Each site will then have at least one on-site visit during the study. Based on the outcome of centralized monitoring activities, the frequency of on-site monitoring activities may be increased. The Monitor will review source documents for verification of consistency with the data recorded in the eCRFs for a random sample of patients. The Monitor will also provide information and support to the Investigator(s).

The centralized monitoring will be used to detect each site's level of compliance in terms of completion of CRF generally but also with focus on critical data (e.g. compliance in randomization to propofol or sevoflurane and date of surgery). The outcome of the statistical checks that will be used will indicate whether increased monitoring activities are needed on a specific site.

In terms of review of completed informed consent, only a random sample of the patients will be checked by the monitor in connection with on-site visit. Site will log all completed informed consents on on-going basis. This log needs to be distributed to the monitor on on-going basis and this will serve as monitoring tool of the consent-

Clinical Study Protocol CAN version FINAL 2.0 Date: 28 Oct 2016 process. If there are signs of that the site does not comply with the specified consent-process, extended site-specific training/ increased monitoring activities will be needed.

All monitoring procedures, including both centralized methods and on-site activities, will be described in the Monitoring Plan which will be compiled in collaboration with the Sponsor.

The study centre may also be subject to quality assurance audit by the Sponsor as well as inspection by the Regulatory Authorities. The Investigator and other responsible personnel must be available during the monitoring visits, audits and inspections and should devote sufficient time to these processes.

The Investigator should provide a curriculum vitae (CV) or equivalent documentation of suitability to be responsible for the study. All Investigators and other responsible personnel should be listed together with their function in the study on the signature list.

17 ETHICS

17.1 INDEPENDENT ETHICS COMMITTEE

It is the responsibility of the Coordinating investigator to obtain approval of the study protocol/protocol amendments, the patient information and the Informed Consent from the IEC before enrolment of any subject into the study.

The written approval from the IEC should be dated and have an attached list of those persons (with names and positions) present at the IEC meeting.

If a study stops prematurely at a study centre for any reason, the IEC must be informed. At the end of the study, the Sponsor should notify the IEC. The Sponsor should file all correspondence with the IEC.

The sponsor should file all correspondence with the IEC.

17.2 ETHICAL CONDUCT OF THE STUDY

Clinical Study Protocol CAN version FINAL 2.0

The study will be conducted in accordance with the protocol, applicable regulatory requirements, GCP and the ethical principles of the Declaration of Helsinki as adopted by the 18th World Medical Assembly in Helsinki, Finland, in 1964 and subsequent versions.

17.3 ETHICAL CONSIDERATIONS INCL RISK EVALUATION

Both propofol and sevoflurane are well established drugs for general anaesthesia with known side effects. The monitoring of the patients during surgery in normal clinical practice is extensive and the study does not add any additional risks for the patient. However, the objective of this study with a potential difference in survival between these hypnotics may worry the patients. It is thus essential that each patient get proper information with time for questions. It is also important to point out that the signs of differences noted in animal studies may potentially not be valid for humans.

Date: 28 Oct 2016 25 (31)

There is no specific gain for the individual patient to participate in the study. However, if the hypothesis in this protocol is correct, approximately 370 more patients will reach 5-year-survial in Sweden if propofol is used instead of sevoflurane. On a global basis with 1,600 000 new breast cancer patients annually, the corresponding number will be 80,000. Then, the study results should have a future impact on the hypnotic procedure in connection with cancer surgery.

The study is justified as the risks with the study are limited and there is a potential benefit on population-level for the patients in one of the treatment groups.

17.4 PATIENT INFORMATION AND INFORMED CONSENT

It is the responsibility of the Investigator to provide each subject with full and adequate verbal and written information about the objectives, procedures and possible risks and benefits of the study. All subjects should be given the opportunity to ask questions about the study and should be given sufficient time to decide whether or not to participate in the study. The written patient information must not be changed without prior discussion with the Sponsor.

The subjects will be notified of their voluntary participation and of their freedom to withdraw from the study at any time and without giving any particular reason. Subjects must also be informed that withdrawing from the study will not affect their future medical care, treatment or benefits to which the subject is otherwise entitled.

The Investigator is responsible for obtaining written Informed Consent from all subjects (or their legally acceptable representatives and/or witnesses, where applicable) prior to enrolment in the study.

The subjects will consent to:

- Participating in the study.
- Personnel concerned at the Sponsor/designee and regulatory authorities to gain full access to hospital records, to control the data collected in the study.
- Recording, collection and processing of data and storing of data in a database.

A copy of the patient information and the Informed Consent form should be given to the subject. The Investigator (or the designated representative) who gave the verbal and written information to the subject shall sign the Informed Consent form. The Investigator should file the signed Informed Consent forms in the Investigator's File for possible future audits and inspections.

18 DATA HANDLING AND RECORD KEEPING

18.1 CASE REPORT FORMS

This study will use eCRF (electronic CRFs). A CRF is required and should be completed for each randomized subject.

The completed CRFs are the sole property of the Sponsor and should not be made available in any form to third parties (except for authorized representatives of appropriate regulatory authorities) without written permission from the Sponsor. A

Clinical Study Protocol CAN version FINAL 2.0

site-specific pdf-copy of all entered data from that site will be provided to each participating site at study end for filing purposes.

The Investigator is responsible for ensuring the accuracy, completeness and timeliness of the data recorded in the CRFs. The CRFs should be completed in accordance with project specific completion guidelines.

Corrections of the eCRF data will be traceable in audit trail. The person changing the eCRF data must enter a reson for change. The site Investigator will sign off and lock for further changes the completed eCRF to confirm the observations recorded according to ICH GCP.

18.2 RECORD KEEPING

To enable audits and evaluations by the Sponsor and inspections by regulatory authorities, the Investigator shall keep records (essential documents) of the study for 10 years after study completion or longer if required by local law. This includes any original source data related to the study, the subject identification list (with subject numbers, full names and addresses), the original signed Informed Consent forms and pdf-copies of all completed eCRFs.

